8.4.2 Secondary endpoints

The secondary endpoints for this study are the following:

- Change in 24-hour mean weighted glucose between Day 1 of Week 10 (Day 64/65) and Day 6 of Week 10 (Day 69/70) within each EQW-treated patient
 - Note that Day 6 data will consist of data from Day 6 \pm 1 day (Days 5 through 7)
 - There will also be an average of change in 24-hour mean weighted glucose from baseline to Days 1 to 6 of Week 10 and Week 4 calculated (SD, MAGE, “Distance travel”, “Energy”)
- Change from baseline (Day 1) to Day 6 of Week 10 (Day 70) and Day 6 of Week 4 (Day 28) in FPG
- Change from baseline (Day -1) to Day 6 of Week 10 (Day 69) and Day 6 of Week 4 (Day 27) in 2-hour mean weighted PPG (after the breakfast meal)

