2.2 Secondary objectives

Secondary Objectives:	Outcome Measures:
To examine the intra-patient variability of the change in 24-hour mean weighted glucose at the beginning and the end of the dosing cycle (Week 10 of treatment in EQW patients), using data obtained by a CGM system	Change in 24-hour mean weighted glucose between Day 1 of Week 10 (Day 64/65) and Day 6 of Week 10 (Day 69/70) within each EQW-treated patient
To compare the effect on fasting plasma glucose (FPG) and 2-hour PPG after 4 and 10 weeks of dosing of EQW plus metformin with placebo plus metformin	Change from baseline (Day 1) to Day 6 of Week 10 (Day 70) and Day 6 of Week 4 (Day 28) in FPG Change from baseline (Day -1) to Day 6 of Week 10 (Day 69) and Day 6 of Week 4 (Day 27) in 2-hour mean weighted PPG (after the breakfast meal)
To compare the following parameters after 4 and 10 weeks of dosing between the EQW plus metformin and placebo plus metformin treatment groups, using data obtained by a CGM system: the effect on 24-hour mean amplitude of glucose excursion (MAGE) the proportion of time patients who had plasma glucose measurements of: <70 mg/dL ≥70 mg/dL and ≤180 mg/dL or >180 mg/dL	Average of change in 24-hour mean weighted glucose from baseline (Day -1/1) to Days 1 to 6 of Week 10 and Week 4 calculated. (standard deviation [SD], MAGE, “Distance travel”, “Energy”)
To compare the effect on HbA1c levels and 2-hour PPG after 4 and 10 weeks of dosing of EQW plus metformin with placebo plus metformin	Change from baseline (Day -1) to Day 6 of Week 10 (Day 69) and Day 6 of Week 4 (Day 27) in 2-hour mean weighted PPG (after the breakfast meal)

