3.5 Methods for assigning treatment groups

At Screening, the site will assign each patient a unique sequential patient number and enter this number into the interactive voice response system/interactive web response system (IVRS/IWRS). The patient number will consist of the letter E and a 7 digit number (the 4 digit site number and 3 digit patient number). This number will be used for identification throughout the study and will not be used for any other participant.

Patients entering the lead-in period

At the time of entry into the lead-in period, the patients will receive a pharmacy card to obtain their metformin XR.

Patients entering the double-blind treatment period

Following completion of the lead-in period, patients eligible for double-blind treatment will be randomly assigned to 1 of the 2 treatment arms by the IVRS/IWRS in a 1:1 ratio using a blocked randomization schedule:

- EQW (BYDUREON [exenatide extended-release for injectable suspension]) + metformin XR
- Placebo injection similar to EQW + metformin XR

The treatment assignment will be balanced within each site by the IVRS/IWRS through block allocation to sites. Randomization schedules will be generated and kept by AstraZeneca. At all study visits when study medication is dispensed, each patient will be assigned a kit number by the IVRS/IWRS. Kit numbers will be recorded on the eCRF. The IVRS/IWRS will be available 24 hours per day, 7 days a week.

If a dose is missed, it should be administered as soon as noticed, provided the next regularly scheduled dose is due at least 3 days later. If the next regularly scheduled dose is due within less than 3 days, then the missed dose should be skipped. Thereafter, patients can resume their usual dosing schedule of once every 7 days (weekly).

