Note: Entry into the lead-in period (Day -28) should occur at least 7 days after Screening but no later than 14 days after receiving the Screening laboratory results. Study visits during the lead-in period and the double-blind treatment period should occur on the designated visit day ± 3 days.

- Screening can be performed over multiple visits. Entry into the lead-in period should occur at least 7 days after Screening and no later than 14 days after screening.
- If the patient discontinues during one of the 7 day CGM periods, remove CGM device. The CGM device should not remain in place longer than 10 days.
- Standard safety blood tests, urinalysis for safety analysis, and HbA1c will be performed 30 minutes prior to the standardized breakfast meal.
- A complete physical examination will be performed on days designated with an X. A brief physical examination will be performed on days designated with an X^d. See Section 5.2.2 for details.

- e. If patient is discontinuing the study due to an adverse event, a 5 mL blood sample for assessment of exenatide plasma concentration will be collected.
- f. See [Table 4](#) for a list of the safety laboratory variables for this study. Patients who discontinue should have a standard safety laboratory panel collected at the conclusion of their participation.
- g. Women of childbearing potential only.
- h. Glucose levels will be drawn 30 minutes before and just prior to breakfast and 30, 60, 120, and 180 minutes after breakfast. The post meal glucose tolerance test is provided in a 3 day window.
- i. Patients must be fasting at this time point.
- j. Includes hepatitis screen panel (anti-hepatitis C virus and HBsAg only).
- k. Patients should be instructed to perform fasting SBGM daily, and instructed to call the site if they have a FPG ≥ 270 mg/dL (15 mmol/L) for 3 consecutive days. The patient should have a FPG by central laboratory; if ≥ 270 mg/dL (15 mmol/L), the patient should be discontinued. If the patient has not performed fasting SBGM and the central laboratory FPG at Day -7 ≥ 270 mg/dL (15 mmol/L), the patient should be considered for discontinuation.

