Prior to the end of this visit, the patient will be scheduled to return on Day 64 (Week 10) for the standardized breakfast meal PPGT test, to occur between 06:00-10:00.

4.2.8 Day 64, Visit 13

Patients are to arrive at their study visit on Day 64 between 06:00-10:00. Study procedures will be performed as listed in Table 2.

The IVRS/IWRS should be notified if the patient is discontinued from the study. Patients will remain at the study site for collection of PK and biomarker blood samples according to the sampling described below:

- Perform PK blood sampling prior to the meal (see Section 5.4).
- Collect blood samples for biomarker analysis prior to the meal (see Section 5.7).

Additionally, samples will be taken from patients for FPG, HbA1c, and safety laboratory assessments. See Table 4 for a list of the safety laboratory variables.

Patients will be provided a standardized breakfast following guidelines at the study site. The standardized breakfast meal should account for approximately 35% of the daily calorie intake (~700 kcal). The meal should be consumed in 30 minutes. These meals will remain consistent across the Day -7, 22, and Day 64 visits. For details on the procedures before and after the breakfast meal, see Section 5.3.1.

Patients will take their dose of double-blind study medication with time of dose noted on the eCRF if the patient is due for their weekly dose of double-blind study medication.

In addition, patients will be reminded:

- Of the fasting requirements for the Day 70 visit (at least 8 hours prior to visit).
- To call the investigative site if the fasting daily glucose on 3 consecutive days is ≥ 270 mg/dL (15 mmol/L).
- That the patient must re-calibrate the CGM system device every 12 hours per manufacturer's instructions.

- To bring study medication and glucose meter to the next scheduled study visit.
- To abstain from tobacco, nicotine, or nicotine replacement therapy alcohol, and caffeine for 24 hours prior to and during the study visits, which include the 24-hour glucose monitoring period.
- The timing and content of meals should remain consistent across the 7-day CGM system monitoring period. See Section 3.8.1 for details.
- To refrain from strenuous exercise, contact sports, and sunbathing for the 24 hours prior to all study site visits.

Prior to the end of this visit, the patient will be scheduled for the next study visit (Day 70 with 68, 69, and 70 window), to occur prior to 18:00.

4.2.9 Day 70, Visit 14

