7.2 Dose and treatment regimens

Double-blind study medication will be administered subcutaneously once weekly (Day 7 each week). The IVRS/IWRS, described in Section 3.5, will be used to assign each patient EQW or placebo, at the appropriate dispensing visits.

Patients will take their first dose of double-blind study medication (EQW or placebo) at the site on Day 1. The time of first dose will be noted on the eCRF. Patients will be trained on IP administration at this visit. The injection must be administered immediately after preparation of the dose.

During the treatment period, patients will take the double-blind study medication once weekly (Day 7 each week). Patients will take metformin XR once daily with the evening meal.

The study design includes the following 2 treatment periods:

Medical nutrition and metformin XR lead-in period

After qualifying for entry into the lead-in period, patients will discontinue their current metformin therapy and begin a 4-week, medical nutrition, and open-label metformin XR lead-in period. Patients will be given pharmacy cards to obtain metformin XR. The dose of metformin XR assigned will correspond with each patient's background dose of metformin. Each patient will be instructed to take:

- Open-label metformin XR: 3-4 tablets with the evening meal (1500-2000 mg)

Compliance with the administration of multiple tablets will be assessed during the lead-in period. Patients must demonstrate good compliance (see Section 7.5) with metformin XR (80% to 120%) during the lead-in period and the ability to have a week-long CGM measurement to be eligible for randomization.

Double-blind treatment period

Following completion of the lead-in period, eligible patients will enter the 10-week, double-blind treatment period.

Patients will be randomized to 1 of 2 treatment arms:

- EQW + open-label metformin XR (1500-2000 mg).
- Placebo + open-label metformin XR (1500-2000 mg).

The double-blind study medication (either EQW or placebo) will be administered subcutaneously once weekly and the metformin XR will be taken once daily with the evening meal.

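### The Week 10 dosing-cycle endpoint is fixed to study days, not to the injection, so a late dose allowed by the missed-dose rule reverses its beginning and end in some patients

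*Protocol*

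**What the plan says.** The first secondary objective (Protocol 2.2) concerns intra-patient variability of 24-hour mean weighted glucose "at the beginning and the end of the dosing cycle (Week 10 of treatment in EQW patients"). Section 8.4.2 turns this into "Change in 24-hour mean weighted glucose between Day 1 of Week 10 (Day 64/65) and Day 6 of Week 10 (Day 69/70"), taken within each EQW patient. Its note widens Day 6 to Days 5 through 7, still counted by study week. Section 8.5.2 makes the summary descriptive, with no test.

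On dosing, 7.2 states: "Patients will take their first dose of double-blind study medication (EQW or placebo) at the site on Day 1". It then places the weekly injection on Day 7 of each week. Section 3.5 says of a missed dose that "it should be administered as soon as noticed, provided the next regularly scheduled dose is due at least 3 days later"; otherwise it is skipped. Patients then "resume their usual dosing schedule of once every 7 days (weekly"). At the Day 64 visit (4.2.8) the injection is taken "if the patient is due for their weekly dose of double-blind study medication", and its time goes on the eCRF. Section 7.5 requires administration of all study drugs to be recorded there.

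**The concern.** The objective is about position in the dosing cycle; the endpoint is about position in the study calendar. The two agree only when the Week 10 injection is given on its due day or close to it. The protocol has a rule for giving it later, and it neither re-labels the two profiles nor sets such patients aside when that rule is used.

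Section 1.2 says the study will assess how well EQW maintains a similar degree of control within a patient at steady state. This endpoint carries that question. If some differences run from beginning to end of a cycle, some from end to beginning, and some across a cycle with no injection, neither the mean change nor its variability describes a dosing cycle.

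**Working it through.** The plan states no figure to reproduce here. The check is calendar arithmetic.

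**Inputs**
- Dosing interval: 7 days (3.5).
- Minimum gap from a late dose to the next scheduled one: 3 days (3.5).
- Due day of the Week 10 dose: Day 1 + 9 × 7 = Day 64 if counted from the first dose; Day 63 if given on Day 7 of each week (7.2). Both are carried through.
- Profiles: Day 64/65 and Day 69/70 (8.4.2).
- Assumption: the previous dose was on time (Day 57 or Day 56).

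**Maximum lateness** = 7 − 3 = 4 days.

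**Days since last injection** = study day − Week 10 injection day, once that injection has been given; before that, study day − (due day − 7).

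| Due | Days late | Injected | Next due in | At Day 64/65 | At Day 69/70 | Order |
|---|---|---|---|---|---|---|
| 64 | 0 | 64 | 7 | 0–1 | 5–6 | as intended |
| 64 | 1 | 65 | 6 | 7, then 0 | 4–5 | mixed |
| 64 | 2 | 66 | 5 | 7–8 | 3–4 | reversed |
| 64 | 3 | 67 | 4 | 7–8 | 2–3 | reversed |
| 64 | 4 | 68 | 3 | 7–8 | 1–2 | reversed |
| 63 | 0 | 63 | 7 | 1–2 | 6–7 | as intended |
| 63 | 1 | 64 | 6 | 0–1 | 5–6 | as intended |
| 63 | 2 | 65 | 5 | 8, then 0 | 4–5 | mixed |
| 63 | 3 | 66 | 4 | 8–9 | 3–4 | reversed |
| 63 | 4 | 67 | 3 | 8–9 | 2–3 | reversed |

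**Skipped dose, due Day 64.** If it is noticed on Day 69, the next dose is 71 − 69 = 2 days away, so it is skipped. Day 64/65 is then 64 − 57 = 7 to 65 − 57 = 8 days after the last injection, and Day 69/70 is 69 − 57 = 12 to 70 − 57 = 13 days. The order is kept, but the cycle is extended.

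**A second route.** Section 3.5 does not say whether the 7-day clock restarts at a late injection. If it does, an earlier dose 4 days late gives injections on Days 54, 61 and 68. Day 64/65 is then 3–4 days and Day 69/70 is 1–2 days after injection. The point does not depend on this reading.

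**Do other rules catch it?** The Day 6 ± 1 note covers Days 68–70 by study day, so it does not realign anything. The Evaluable set (8.3.1) requires completion and procedural compliance but names no injection-timing criterion. Section 7.5 judges EQW compliance from used vials, which show that a dose was taken, not when.

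**The case against.** Long delays should be uncommon. Patients attend on Days 57, 63 and 64 and bring their study medication, compliance is reviewed, and a due dose is taken at the visit. With visits on the designated days, a dose reaches Day 67 or 68 only if both patient and site overlook it. This stands, and it limits how many patients are affected. It does not remove the case, because 3.5 provides for it.

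Only the missed-dose rule produces the delay. The wording "if the patient is due for their weekly dose of double-blind study medication" does not authorise one, and the visit window ("Study visits during the lead-in period and the double-blind treatment period should occur on the designated visit day ± 3 days") enters no line of the arithmetic. Both remarks are right, and nothing here rests on either. Patients who inject on time are correctly labelled on both dosing calendars.

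The SAP, not shown, could map study days to dose times, since 5.1.1.1 leaves calculation detail to it. But the days themselves are fixed in the protocol, so anchoring to the injection changes a stated endpoint definition; it does not fill in a detail left open.

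A reader might infer that crossed labels pull the mean change toward zero and so manufacture flat control, or apply a simple dilution factor to show it. The documents do not support that. They give no rate of late doses. A 7–8 versus 1–2 day comparison is not the mirror image of 0–1 versus 5–6. Skipped doses keep the order and, if control wanes after injection, push the change away from zero. Extra spread would argue against flat control, not for it.

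**Conclusion.** The point holds for a limited group. For EQW patients whose Week 10 injection is at least 2 days late (due Day 64) or at least 3 days late (due Day 63), up to the permitted 4, the endpoint's beginning and end are reversed. For a skipped dose due on Day 64, the end profile falls 12–13 days after the last injection. These results assume that the previous dose was on time.

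The number affected cannot be derived from the protocol and is probably small. The net direction of bias is unknown. Because the summary is descriptive and outside the testing hierarchy, Type I error and power are untouched, and a reader should not infer any threat to the primary comparison. What suffers is the interpretation of the within-cycle change and its variability. The correction is cheap enough to be worth making.

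**What to change.** In 2.2 and 8.4.2, define the beginning-of-cycle and end-of-cycle 24-hour profiles by elapsed time from the recorded Week 10 injection. The windows can be those an on-time patient already has: 0–1 and 5–6 days if Day 64 is the due day, 1–2 and 6–7 if Day 63. Carrying the existing ± 1 day tolerance over to elapsed time keeps a patient who is one day late, whose Day 69/70 profile lies at 4–5 or 5–6 days respectively.

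Report separately, with their number, EQW patients who have no injection near the start of the monitoring week. Keep the study-day version as a supportive summary, so that all Modified ITT patients on EQW with data still appear.

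The sponsor must also reconcile the Day 1 first dose with the Day 7 weekly dosing day in 7.2, because the windows depend on it. No dosing or missed-dose rule is proposed here, and the sensor schedule can stay.

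The cost is endpoint wording and a derivation from dose times already required on the eCRF. The downside is that a few patients contribute no aligned pair to this summary. No randomised comparison is affected, since the summary is within the EQW arm.

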3.8.1 Dietary guidance/restrictions

Beginning in the lead-in period, and continuing throughout the study, patients will be asked to follow instructions on medical nutrition in accordance with the American Diabetes Association (ADA) dietary guidelines or locally accepted guidelines. Patients will be provided with instructional material and training regarding the medical nutrition guidelines. Patients will be asked to follow a standard diabetic weight maintaining diet containing approximately 55% carbohydrate, 25% fat, and 20% protein. The total daily caloric intake for each patient will be limited to approximately 2000 kcal.

The timing and content of meals should remain consistent across the 7-day CGM system monitoring period. The timing and content of meals should be similar from the 7-day CGM testing at baseline vs. CGM testing during the treatment period to ensure comparability of data.

In order to keep the timing and content of meals consistent patients should avoid significant changes during 7-day CGM assessments (i.e., typical portion sizes, same pattern/meals when dining at restaurants, avoiding holidays/celebratory meals, etc).

Patients will be provided a standardized breakfast meal following guidelines at the study site on Day -7, Day 22, and Day 64. The standardized breakfast meal should account for approximately 35% of the daily calorie intake (~700 kcal). After the meal is given, only water will be provided through the completion of the meal test.

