- To take their open-label metformin XR and their dose of double-blind study medication with time of dose noted on the eCRF if the patient is due for their weekly dose of double-blind study medication.

4.2.7 Day 63, Visit 12

Patients are to arrive at their study visit prior to 16:00 on Day 63. Study procedures will be performed as listed in [Table 2](#). The IVRS/IWRS should be notified if the patient is discontinued from the study. The patient will obtain his or her fingerstick blood glucose level and input it to the CGM sensor as calibration points.

The CGM system sensor will be inserted, and confirmation that the system is working properly will be obtained. Patients will be sent home with instructions regarding calibration 2 hours after insertion, post dinner, before bedtime, and a fasting assessment the next morning, then calibrate every 12 hours (see Section [5.2.6.2](#)). Patients should be reminded that the timing and content of meals should remain consistent across the 7-day CGM system monitoring period. See Section [3.8.1](#) for details on the meals. The SBGM measurements/records, and the calibration and function of the CGM system device should be reviewed.

In addition, patients should be reminded:

- Of the fasting requirements for the Day 64 visit (at least 8 hours prior to visit).
- To bring study medication and glucose meter to the next scheduled study visit.
- To call the investigative site if the fasting daily glucose on 3 consecutive days is ≥ 270 mg/dL (15 mmol/L).
- That the patient must re-calibrate the CGM system device every 12 hours per manufacturer's instructions.
- To bring study medication and glucose meter to the next scheduled study visit.
- To abstain from tobacco, nicotine or nicotine replacement, alcohol, and caffeine for 24 hours prior to and during the study visits, which include the 24-hour glucose monitoring period.

- The timing and content of meals should remain consistent across the 7-day CGM system monitoring period. See Section 3.8.1 for details.
- To refrain from strenuous exercise, contact sports, and sunbathing for the 24 hours prior to all study site visits.
- To take their open-label metformin XR and their dose of double-blind study medication with time of dose noted on the eCRF if the patient is due for their weekly dose of double-blind study medication.

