5.3 Other assessments

5.3.1 Procedures before and after the standardized breakfast meal

- The time of commencement of the breakfast meal on the day of the visit will be considered the 0 time point for all testing. Note: There is a window of ± 2 minutes for sampling time points.
- At 60 minutes prior to the breakfast meal, confirm CGM system device is functioning properly.

- At 30 minutes prior to the breakfast meal, obtain blood specimens for glucose and standard safety assessments. Have the patient void urine (use this specimen for the urinalysis for the standard safety labs).
- On Day 22 and Day 64, perform PK blood sampling and biomarker analysis (prior to the breakfast meal).
- The time T1 = -30 will mark the beginning of the 24-hour blood glucose collection.
- Just prior to the breakfast meal, obtain blood specimens for glucose, insulin, glucagon, and C-peptide.
- The patient should consume the entire meal within 30 minutes. Note the time the meal was started and completed. Record on the eCRF.
- Obtain blood specimens for glucose, insulin, and c-peptide at 30, 60, 120, and 180 minutes following the breakfast meal.

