8.5.2 Analysis of the secondary variable(s)

Intra-patient difference and variability of the 24-hour weighted mean glucose between Day 1 and Day 6 of Week 10 will be calculated and presented descriptively; no hypothesis testing will be performed.

The change in FPG from baseline (Day 1) to Day 6 of Week 10 (Day 70) and Day 6 of Week 4 (Day 28), and the change in 2-hour mean weighted PPG (after the breakfast meal) from baseline (Day -1) to Day 6 of Week 10 (Day 69) and Day 6 of Week 4 (Day 27) will be analyzed using a similar MMRM model as the one described for the primary endpoints; except for the analysis of the endpoint of FPG, the baseline FPG will replace the baseline 24-hour mean weighted glucose as one of the fixed effects.

The change in HbA1c from baseline (Day 1) to Day 6 of Week 10 (Day 70) will be analyzed using an analysis of covariance (ANCOVA) model with treatment as a factor and baseline HbA1c as a covariate.

In order to control the family-wise Type I error, a sequential testing procedure will be implemented. In the hierarchical testing order, the primary endpoints of 24-hour mean weighted glucose at Week 10 will be tested first, followed by 24-hour mean weighted glucose at Week 4, then the secondary endpoints: FPG at Week 10, 4-hour mean weighted glucose at Week 10, then FPG at Week 4, and 4-hour mean weighted glucose at Week 4.

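### The Week 10 start-to-end-of-cycle change is summarised in EQW patients alone, although the meal test and sensor age also differ between the two days

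*Protocol*

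**What the plan says.** Section 1.2 of the protocol sets out to see how well EQW holds a similar degree of control in an individual patient once steady state is reached. Section 2.2 turns this into an objective on intra-patient variability "at the beginning and the end of the dosing cycle (Week 10 of treatment in EQW patients), using data obtained by a CGM system". Section 8.4.2 fixes the measure as the change "between Day 1 of Week 10 (Day 64/65) and Day 6 of Week 10 (Day 69/70) within each EQW-treated patient", with Day 6 data drawn from Days 5 to 7 of the week. Section 8.5.2 says the difference and its variability "will be calculated and presented descriptively; no hypothesis testing will be performed".

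The schedule around the two days is as follows.

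- **Meal test.** Section 3.8.1: "Patients will be provided a standardized breakfast meal following guidelines at the study site on Day -7, Day 22, and Day 64". The breakfast is about 700 kcal, 35% of daily intake, followed by water only until the test ends. Section 5.3.1 adds: "The time T1 = -30 will mark the beginning of the 24-hour blood glucose collection". The note to Table 3 and Section 5.1.2.1 allow a 3-day window for the test.
- **Sensor.** Under Day 63, Section 4.2.7: "The CGM system sensor will be inserted, and confirmation that the system is working properly will be obtained". Calibration follows at 2 hours, after dinner, at bedtime and the next morning, then every 12 hours. Section 4.2.9 has the sensor removed on Day 70.
- **Who is measured.** The notes to Figure 1 in Section 1.4 have all patients, placebo included, wearing the sensor from Day 63 to Day 70. Table 2 gives both arms the same meal-test visit.

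**The concern.** The endpoint serves the question in Section 1.2, whether control is held across the weekly dosing interval. Its mean will naturally be read that way: a rise as waning, no change as maintenance.

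The early reading, however, is scheduled with a clinic test meal and a new sensor, and the late reading has no test meal and an older sensor. Within the EQW arm these differences run alongside the dosing cycle, and enrolling more patients does not separate them. If the meal-test day runs high, control can appear to improve towards the end of the cycle while drug effect is waning; if it runs low, the reverse. A null result could come from offsetting effects. The placebo arm goes through the same days, yet the named endpoint does not use it.

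**Working it through.** **1. The two readings side by side**

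| Feature | Day 64/65 | Day 69/70 | Source |
|---|---|---|---|
| Clinic meal test | Scheduled Day 64, 3-day window | None | 3.8.1, Tables 2 and 3 |
| Meal inside the 24-hour profile | Yes, if the test is on Day 64: start is 30 minutes before the meal | No test meal | 5.3.1 |
| Sensor age | About 1 day | About 6 to 7 days | 4.2.7, 4.2.9, 5.2.6.2 |
| Calibration | Dense first evening and next morning | Every 12 hours | 4.2.7 |
| Fasting reminder, at least 8 hours | Yes | Yes, for Day 70 | 4.2.7, 4.2.8 |
| Data in placebo patients | Yes | Yes | 1.4, Table 2 |

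The meal test, sensor age and calibration differ between the days. Fasting does not.

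**2. The plan's own figure**

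The protocol states no power or precision for this endpoint. The nearest figure is in Section 8.2: 39 per arm, difference 18 mg/dL, SD 24 mg/dL, two-sided 0.05, 90% power at Week 4. The noncentrality is 18 / (24 × √(2/39)) = 3.31, and the t-test power is 90.5%, so the stated figure reproduces. The 18 mg/dL is a between-arm planning effect. It gives scale only and is not a threshold for a within-week change.

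**3. Possible size of the day effects (all assumed)**

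- Meal: shift in the 24-hour mean = m × h / 24. With m = 10 mg/dL and h = 2 hours, 10 × 2 / 24 = 0.8 mg/dL. With m = 60 and h = 4, 60 × 4 / 24 = 10 mg/dL.
- Sensor: shift = relative bias × mean glucose. With 2% at 140 mg/dL, 2.8 mg/dL. With 10% at 180 mg/dL, 18 mg/dL.

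If both act in the same direction, the range is 3.6 to 28 mg/dL. The width of that range shows how little the documents settle.

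**4. What the placebo contrast removes**

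Let c be the drug's start-to-end-of-cycle change, s the part due to sensor age, calibration and other shared day effects, and m_E and m_P the rise that the test meal adds to the Day 64/65 mean in each arm. Then:

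- EQW change = c − m_E + s
- Placebo change = −m_P + s
- Difference = c − (m_E − m_P)

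The shared part s cancels. The meal part cancels only if m_E = m_P. At the extreme where the drug abolishes the meal rise (m_E = 0), the difference is c + m_P, so under the assumptions in step 3 the full 0.8 to 10 mg/dL would remain.

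**5. Consequence when the artefact is common to both arms**

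This simulation of 20,000 trials has 39 patients per arm, no cycle effect, and the same artefact in both arms. No SD for the within-week change is given, so 12 and 24 mg/dL are assumed. The table shows how often a 95% CI excludes zero.

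| Artefact (mg/dL) | EQW alone, SD 12 | EQW alone, SD 24 | EQW − placebo, either SD |
|---|---|---|---|
| 4 | 53% | 17% | 5% |
| 8 | 98% | 53% | 5% |
| 12 | 100% | 87% | 5% |

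The 5% holds because the artefact was made common to both arms. Step 4 shows when that fails.

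**6. Precision cost**

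95% CI half-widths with n = 39 per arm:

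- EQW alone, t(38) × SD / √39: 3.9 mg/dL at SD 12, 7.8 at SD 24.
- EQW minus placebo, t(76) × SD × √(2/39): 5.4 mg/dL at SD 12, 10.8 at SD 24.

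**7. A related ambiguity**

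Section 7.2 gives the first dose on Day 1 but weekly dosing on Day 7. Seven-day steps from Day 1 reach Day 64; Day 7 of each week gives Days 63 and 70. It is therefore unclear whether Day 64 is a dosing day, and whether the Days 5 to 7 window reaches the next dose. These passages must be reconciled before either reading can be called the beginning or end of a cycle.

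**The case against.** The best defence is that the endpoint claims little. It describes each treated patient's own stability, carries no test and sits outside the hierarchy, and nowhere does the protocol say the difference will be attributed causally to the dosing cycle. A between-arm mean answers a somewhat different question. This lowers the stakes, and it is the reason to keep the EQW summary. It does not make the EQW mean interpretable for the purpose stated in Section 1.2, since leaving out a test does not remove a day effect.

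Second, much of the control information is already planned. Section 2.4 describes daily Week 10 values within and between arms, Section 8.4.3 lists lead-in against Week 10 profiles, and Section 8.5.3 summarises and plots both weeks. That stands, so it would be wrong to infer that the placebo and lead-in data go unused. But none of these defines a matched Day 1 to Day 6 change with a between-arm difference.

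Third, the two days are more alike than they first appear. Day 70 is also a clinic visit, with the same 8-hour fasting reminder. Section 3.8.1 asks for consistent meals across the CGM week. The meal window and the Days 5 to 7 window blur the contrast further. All of this stands. The meal window makes the meal effect variable from patient to patient, not absent, and nothing requires the home breakfast to match the clinic meal.

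Fourth, exenatide itself alters the postprandial response and slows gastric emptying (Section 1.1), so the placebo contrast may leave a treatment-by-meal effect behind. This is correct and limits what the remedy can claim.

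**Conclusion.** The concern holds in a limited form. An EQW-only mean change between Day 64/65 and Day 69/70 cannot by itself show maintained or waning control over the dosing cycle, because the scheduled meal test, sensor age and calibration density also differ between the readings.

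Its size is unknown. The assumed meal effect of 0.8 to 10 mg/dL and sensor effect of 2.8 to 18 mg/dL are illustrations; the documents support neither a particular shift nor its direction.

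Two stronger readings are tempting, and the documents support neither. One is that the design has been shown to hide or create a cycle effect of a stated fraction of the planned 18 mg/dL; that fraction would rest wholly on assumed meal and sensor shifts. The other is that EQW minus placebo isolates the cycle effect; it removes only what the arms share.

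The endpoint is descriptive, and this point touches neither the primary endpoints nor Type I error control. It is a cheap improvement in interpretability.

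**What to change.** In Sections 8.4.2 and 8.5.2:

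- Keep the within-patient EQW summary.
- Compute the same Day 64/65 to Day 69/70 change in placebo patients and report EQW minus placebo with a 95% CI, descriptively and outside the testing hierarchy. Label it as the change adjusted for day effects common to both arms.
- State that a drug-modified response to the test meal would remain in this difference.
- As support, report the matching lead-in change, from the meal-test day to the last complete CGM day before sensor removal. The lead-in uses the same meal and calibration scheme before any randomised treatment, so it also gives a direct view of the day effect. It carries the same limit on meal response.
- Add a sensitivity analysis that replaces the meal-test day with the first Week 10 CGM day without a meal test. This removes the meal difference, but not all of the sensor-age difference, and it shortens the span by about a day when the test falls on Day 64.

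The cost is protocol or SAP wording and one extra table from data already collected, with no alpha spent. The between-arm interval is wider than that of the EQW-only mean, by a factor of about 1.4 (5.4 / 3.9 or 10.8 / 7.8) under the assumed SDs.
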